- 14. Presence of risk for increased or uncontrolled bleeding and/or risk of bleeding that is not managed optimally and could place a participant at an increased risk for intraoperative or postoperative bleeding. These could include, but are not limited to, anatomical factors at or near the LP site (e.g., vascular abnormalities, neoplasms, or other abnormalities) and underlying disorders of the coagulation cascade, platelet function, or platelet count (e.g., hemophilia, Von Willebrand's disease, liver disease).
- 15. Presence or anticipated need of an implanted shunt for the drainage of CSF or an implanted CNS catheter at any time during the study.
- 16. Presence or anticipated need of an implanted intravenous port/catheter at any time during Part 1 of the study.
- 17. Clinically significant abnormalities in hematology or blood chemistry parameters, as determined by the Investigator that would render the participant unsuitable for enrollment.

- 18. Clinically significant, as determined by the Investigator, 12-lead ECG abnormalities, including corrected QT interval using Fridericia's correction method of > 450 msec for males and > 460 msec for females.
- 19. In participants in Cohorts A, B, and C1, prescreening ALSFRS-R slope > -0.4 points/month, where prescreening ALSFRS-R slope is defined as: (ALSFRS-R score at Screening 48) / (months from date of symptom onset to date of Screening). This criterion is not applicable for Cohorts C2, D1, and D2.

Medications

- 20. Treatment with another investigational drug (including investigational drugs for ALS through compassionate use programs) or biological agent within 1 month or 5 half-lives of study agent, whichever is longer, before Screening.
- 21. Treatment with an approved disease-modifying therapy for ALS other than riluzole or edaravone within 1 month or 5 half-lives of therapy, whichever is longer, before completion of Screening.
- 22. Treatment with an antiplatelet or anticoagulant therapy that cannot safely be interrupted for LP according to local standard of care and/or institutional guidelines, in the opinion of the Investigator or Prescriber.

Other

- 23. Female participants who are pregnant or currently breastfeeding and those intending to become pregnant during the study.

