19. In participants in Cohorts A, B, and C1, pPrescreening ALSFRS-R slope > -0.4 points/month, where prescreening ALSFRS-R slope is defined as follows: (ALSFRS-R score at Screening – 48) / (months from date of symptom onset to date of Screening)-in participants from Cohorts A, B, C1, and D1. This criterion is not applicable for Cohorts C2, D1, and D2.

Rationale: The original intent of this exclusion criterion was to enrich the study population for faster-progressing participants, but ALSFRS-R prescreening slope has not been found to accurately predict disease progression due to nonlinear progression on the scale. Therefore, this exclusion criterion has been removed to allow participants who would otherwise be eligible to participate in the study.

Section 6.2.1, (Exclusion Criteria) Part 1

Change: A new exclusion criterion was added to restrict allowable ALS treatment for study participants.

Now reads:

21. Treatment with an approved disease-modifying therapy for ALS other than riluzole or edaravone within 1 month or 5 half-lives of therapy, whichever is longer, before Screening.

Rationale: This change ensures that the concomitant disease-modifying medications for ALS that are allowed in Study 275AS101 Part 1 are consistent for all cohorts, to enable pooling of placebo data from participants across cohorts for analysis.

This change also affects Section 7.7.1.2, Disallowed Concomitant Therapy.

Section 6.2.2, (Exclusion Criteria) Part 2

Change: Language was added to permit participants who contracted HIV, HBV, or HCV during Part 1 to continue into Part 2 if appropriate.

Now reads:

- 1. History or positive test result at Screening for HIV. The requirement for testing at Screening may be omitted if it is not permitted by local regulations. If participants from Cohorts D1 and D2 who would seamlessly roll from Part 1 into Part 2 test positive for HIV during screening for Part 2 but are clinically asymptomatic, they may enroll in Part 2 at the discretion of the Investigator.
- 2. Current hepatitis C infection (defined as positive HCV antibody and detectable HCV RNA). Participants with positive HCV antibody and undetectable HCV RNA are eligible to participate in the study. If participants from Cohorts D1 and D2 who would seamlessly roll from Part 1 into Part 2 test positive for hepatitis C during screening for Part 2 but are clinically asymptomatic, they may enroll in Part 2 at the discretion of the Investigator.

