For each of the 100 imputed datasets, change from baseline will be calculated using the imputed datasets, and the change from baseline endpoint will be compared between treatment groups (BIIB105 60 mg vs Pooled Placebo 1+2 and BIIB105 120 mg vs Pooled Placebo 1+2) using an ANCOVA model for continuous endpoints (████████ and pharmacodynamic endpoints). The ANCOVA model will include covariates for each of the corresponding baseline value for the endpoint, baseline plasma NfL, ██████████

████████ The model will be used to present overall LS means and standard errors for each treatment group (Pooled Placebo 1+2, BIIB105 60 mg and BIIB105 120 mg), and LS mean differences for treatment (BIIB105 60 mg vs Pooled Placebo 1+2 and BIIB105 120 mg vs Pooled Placebo 1+2) with corresponding 95% CI and p-values. A combined estimate of the LS means, LS mean differences and standard errors of the 100 imputed datasets will be obtained, where standard errors will be used to obtain 95% CI from PROC MIANALYZE [Little et al, 2002]. Separate ANCOVA models will be used to obtain estimates, 95% confidence intervals and p-values for other visits. ██████████

For analyses of Part 1, ANCOVA model will be performed to compare BIIB105 60 mg vs. Pooled Placebo 1+2 and BIIB105 120mg vs. Pooled Placebo 1+2.

As scheduled visits are different between cohorts A, B, C1, C2 and cohorts D1, D2, scheduled visits from cohorts A, B, C1, C2 might be combined with selected scheduled visits from cohorts D1, D2 when placebo participants from different cohorts are pooled to perform descriptive analysis, multiple imputation and ANCOVA.

CONFIDENTIAL

The information contained herein may not be used, disclosed, or published without the written consent of
Biogen MA Inc.

Table 12 Scheduled Visits from Different Cohorts – Part 1

Endpoints	Scheduled Visits Cohort A, B, C1, C2	Scheduled Visits Cohort D1, D2	Visits Combination
PD biomarkers	Baseline, 29, 57, 85, 130, 175	Baseline, 29, 57, 85, 113, 141, 169	Day 130/141, Day 169/175

CONFIDENTIAL

The information contained herein may not be used, disclosed, or published without the written consent of
Biogen MA Inc.

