The information contained herein may not be used, disclosed, or published without the written consent of Biogen MA Inc.

Table 13: Seed used for each PD endpoint in MI

Endpoint	Seed
Plasma NfL	3847243

Statistical Analyses

For the statistical analysis of PD biomarkers, the data will be transformed using the natural logarithmic scale.

The following statistical analyses will be evaluated in PD population:

For analyses of Part 1, ANCOVA model will be performed for BIIB105 60 mg vs. Pooled Placebo 1+2 and BIIB105 120 mg vs. Pooled Placebo 1+2.

An ANCOVA model for log ratio to baseline will be performed on change from baseline values on log scale (i.e. $\log(\text{postbaseline}) - \log(\text{baseline})$) for each of the 100 imputed datasets for each PD biomarker. The model will include covariates for the corresponding baseline value, i.e. log value, baseline disease duration since symptom onset, and use of riluzole or edaravone. The least square (LS), i.e. adjusted mean of each treatment group, as well as the treatment group differences will be presented with 95% confidence intervals (CIs) and the p-value.

The following plots over time will be presented for each PD biomarker using the MI imputed datasets where appropriate:

- Arithmetic mean ratio to baseline with standard error bars
- Geometric mean ratio to baseline with standard error bars

Listing of individual data will also be provided.

CONFIDENTIAL

The information contained herein may not be used, disclosed, or published without the written consent of Biogen MA Inc.

CONFIDENTIAL

CONFIDENTIAL

CONFIDENTIAL

CONFIDENTIAL

6. Changes from Protocol-Specified Analyses

- As we do not expect to see many events during the 6 month period, we remove the time to event analyses since symptom onset.

7. References

Protocol 275AS101 Protocol Version 5.0

275AS101 Unblinding Plan Version x.0

CONFIDENTIAL

The information contained herein may not be used, disclosed, or published without the written consent of
Biogen MA Inc.

[REDACTED]

[REDACTED]

[REDACTED]

CONFIDENTIAL

The information contained herein may not be used, disclosed, or published without the written consent of
Biogen MA Inc.

APPENDICES

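### The Part 1 PD ANCOVA pools placebo across cohorts with different slope criteria and has no slope or cohort term, so the 60 mg and 120 mg contrasts can be biased in opposite directions by an unknown amount

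*SAP*

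**What the plan says.** **Contrasts.** Section 5.9 of the Part 1 SAP sets two PD comparisons: "ANCOVA model will be performed for BIIB105 60 mg vs. Pooled Placebo 1+2 and BIIB105 120 mg vs. Pooled Placebo 1+2". The general ANCOVA text before Section 5.6.2 repeats them. Section 5.1 makes Pooled Placebo 1 the placebo participants of A, B, C1 and D1, and Pooled Placebo 2 those of C2 and D2. Per Section 5.7, 60 mg is C1+C2 and 120 mg is D1+D2.

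**Covariates.** For PD markers, besides the marker's own log baseline, the model takes "baseline disease duration since symptom onset, and use of riluzole or edaravone". In the general text the list begins "The ANCOVA model will include covariates for each of the corresponding baseline value for the endpoint, baseline plasma NfL" and is then redacted.

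**Entry rule.** Protocol Section 6.2.1, criterion 19, excludes on slope: "In participants in Cohorts A, B, and C1, prescreening ALSFRS-R slope > -0.4 points/month". It adds: "This criterion is not applicable for Cohorts C2, D1, and D2".

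**History.** The Version 4.0 amendment summary shows that D1 was under the same rule until then. On its purpose it says: "The original intent of this exclusion criterion was to enrich the study population for faster-progressing participants". The rule was dropped for D1 because the slope had not proved an accurate predictor, decline on the scale being nonlinear. The same amendment raised D1 from 20 to 48 participants.

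**Availability.** Part 1 SAP Section 5.3 already summarises a pre-screening slope at baseline.

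**The concern.** Randomisation protects comparisons within a cohort. It does not make a dose group comparable with placebo participants from cohorts that had other entry rules. Here the dose groups and their common control differ by design in how many participants passed a screen meant to select faster progressors, and the PD model contains nothing that identifies this.

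The amendments show that the sponsor cared about this kind of comparability. Version 4.0 aligned permitted ALS therapy across cohorts, and Version 3.0 kept the Part 1 ban on indwelling ports, both partly so that placebo could be pooled. Version 4.0 nevertheless removed the slope rule for D1.

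At stake is the reading of change in plasma NfL, a secondary endpoint, and of CSF ATXN2. If screened and unscreened participants would differ untreated, part of an estimated 120 mg effect, or of a masked one, comes from the entry criteria, with the opposite error at 60 mg.

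**Working it through.** **Inputs** (planned sizes, Protocol Section 5.3.1)

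| Cohort | Active | Placebo | Slope rule now |
|---|---|---|---|
| A | 6 | 2 | yes |
| B | 6 | 2 | yes |
| C1 | 9 | 3 | yes |
| C2 | 3 | 1 | no |
| D1 | 36 | 12 | no |
| D2 | 12 | 6 | no |

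**Check on the plan's figures.** Placebo in A, B, C1 and D1 is 2+2+3+12 = 19, the N in the first NfL power statement. All placebo is 26, all 120 mg active is 48, and the total is 98. The power figures themselves are redacted and cannot be reproduced.

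**Slope-screened shares, current criterion**
- 60 mg: 9/(9+3) = 75%
- Pooled Placebo 1+2: (2+2+3)/26 = 7/26 = 26.9%
- 120 mg: 0/48 = 0%

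**Bias of a contrast** = (screened share in active - screened share in placebo) x delta. Delta is the covariate-adjusted untreated difference in log ratio to baseline, screened minus unscreened. Negative bias lowers the marker on drug relative to placebo.
- 120 mg: 0 - 0.269 = -0.269 delta
- 60 mg: 0.750 - 0.269 = +0.481 delta

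**If the first 20 D1 participants (15:5 at 3:1) entered under the earlier rule**
- Placebo: (7+5)/26 = 46.2%; 120 mg: 15/48 = 31.3%
- 120 mg: 0.3125 - 0.4615 = -0.149 delta
- 60 mg: 0.750 - 0.4615 = +0.288 delta

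The 120 mg imbalance disappears only when 36f/48 = (7+12f)/26, that is f = 0.933 of D1 screened. Twenty of 48 is 42%.

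**What this does to error rates.** With SE = SD x sqrt(1/n1 + 1/n2), the SE is 0.244 SD for 48 vs 26 and 0.349 SD for 12 vs 26. The table assumes no true effect and a two-sided 5% test (the level in the power statements is redacted), and gives the chance of a significantly lower marker on drug, nominally 2.5%. The values of delta are assumptions.

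| Delta | 120 mg, current rule | 60 mg, current rule | 120 mg, 20 screened | 60 mg, 20 screened |
|---|---|---|---|---|
| +0.50 SD | 8.0% | 0.4% | 4.9% | 0.9% |
| +0.25 SD | 4.6% | 1.1% | 3.5% | 1.5% |
| 0 | 2.5% | 2.5% | 2.5% | 2.5% |
| -0.25 SD | 1.3% | 5.3% | 1.7% | 4.0% |

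**How much the existing covariates absorb.** A simulation used 2,000 trials per scenario, D1 wholly unscreened, and fairly strong assumed correlations: slope with progression 0.6, progression with outcome 0.6, progression with baseline NfL 0.5. Riluzole and edaravone use was not modelled. Monte Carlo error is about 0.006 to 0.008 SD.

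| Model | Bias 120 mg | Bias 60 mg |
|---|---|---|
| No covariates | -0.052 SD | +0.088 SD |
| Baseline marker and disease duration | -0.026 SD | +0.050 SD |
| The same plus slope | -0.003 SD | +0.003 SD |

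The middle row implies an adjusted delta near 0.1 SD (0.026/0.269 = 0.097; 0.050/0.481 = 0.104). Its biases are about 0.11 and 0.14 of the SE (0.026/0.244; 0.050/0.349). With no correlation between slope and progression, every model gave about 0.01 SD, with no detectable tilt.

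**PolyQ mix** does not drive this: 3/12 = 25%, 12/48 = 25% and 7/26 = 27%.

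**The case against.** The strongest reply is that nothing in the documents links prescreening slope to change in NfL or ATXN2, and that the sponsor dropped the rule because the slope predicted poorly. The model also adjusts for baseline marker and for disease duration, which is essentially the slope's denominator. On the simulated assumptions, what remains is about a tenth of a standard error at 120 mg. This stands as an argument that the bias may be small. It does not show that it is zero: inaccurate prediction is not absence of association.

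Two further points stand in part. Some D1 participants may have been screened, which shrinks both multipliers without changing their signs unless about 93% were. And the Part 2/integrated SAP compares 120 mg with D1+D2 placebo alone, but for clinical function, at Week 40 after placebo participants could cross over. Its Section 5.9 plans no PD analysis.

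A reader might infer more than the documents support:
- *The 120 mg contrast is tilted towards drug and the 60 mg contrast against it.* That needs a positive delta. A negative one reverses both.
- *The ALSFRS-R, SVC and HHD analyses also omit slope.* The general covariate list is partly redacted, so the omission can be verified only for PD. Later sections are redacted too, so a further sensitivity analysis may exist. The one visible for PD excludes outliers.
- *The plan manufactures a dose response.* No 60 vs 120 mg test is specified in the PD section, and the last Part 1 dose is Day 85 in one group and Day 169 in the other.
- *This bias drove the decision to stop.* The integrated SAP reports no neurofilament effect and no clinical benefit, so a false benefit did not drive it.

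**Conclusion.** The concern holds as a possible bias of unknown sign and size, confined to the Part 1 PD ANCOVA. It is certain that the slope rule differs across the pooled cohorts and that the PD model has no slope or cohort term. At planned sizes the two contrasts carry -0.27 and +0.48 times delta, or about -0.15 and +0.29 if 20 D1 participants were screened. In both cases the signs are opposite for any nonzero delta.

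Delta is not in the documents. At an assumed adjusted value of 0.1 SD the effect is minor; at 0.25 to 0.5 SD it would alter the 120 mg false-positive rate materially. These results rest on planned rather than actual numbers, a common SD, and a purely additive difference between screened and unscreened participants. The change is worth making because it is nearly free and removes a question that the present model cannot answer.

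**What to change.** 1. Add prescreening ALSFRS-R slope as a covariate in the Part 1 PD ANCOVA and in its imputation model. It follows from the Screening score and symptom-onset date, which every cohort provides. The cost is one model degree of freedom and a sentence in the SAP.

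2. Add a sensitivity analysis of 120 mg against D1+D2 placebo only. The SE rises by sqrt((1/48+1/18)/(1/48+1/26)) = 1.135, about 14%. The slope imbalance becomes 0 under the current rule, or 15/48 - 5/18 = +0.035 if 20 D1 participants were screened. A D1/D2 term would keep the comparison within randomised cohorts, since their allocation ratios differ.

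3. Report how many D1 participants, by arm, entered under the earlier criterion.

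4. A comparison of 60 mg with A+B+C1+C2 placebo (12 vs 8) may be shown for information. Its SE is about 31% larger (sqrt((1/12+1/8)/(1/12+1/26)) = 1.308), and it leaves 75% against 7/8 = 87.5% screened. It should not gate any conclusion.

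If Part 1 is already unblinded, label these analyses post hoc. The integrated SAP of September 2024 indicates that it is, since it cites Part 1 results as grounds for termination.

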Appendix 1: Derivation of Demographic and Baseline Characteristics

BMI will be calculated as weight (kg) / height² (m²).

Time since ALS symptom onset will be calculated in months as (date of first dose received – date of ALS symptom onset)/30.4375. Time since ALS diagnosis will be calculated in months as (date of first dose received – date of ALS diagnosis)/30.4375. For the purpose of these calculations partial dates for ALS symptom onset or ALS diagnosis will be imputed as follows: missing day will be imputed with 15th and missing month/day will be imputed with January 15th.

[REDACTED]

Partial dates for symptom onset will be handled as defined above.

CONFIDENTIAL

The information contained herein may not be used, disclosed, or published without the written consent of Biogen MA Inc.

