13.3.4. Clinical Function and Quality of Life Measures

The actual scores and changes from baseline in each measure will be summarized using descriptive statistics. Missing data will be imputed using multiple imputation. Multiple imputation will be performed on actual values, domains, total scores, or summary scores depending on the endpoint. In addition, each clinical function measure will be analyzed using an ANCOVA model. The model may include covariates such as corresponding baseline value, baseline NfL, duration from onset of symptoms to the first dose of study treatment, and riluzole or edaravone use. The model will be used to estimate least-square (LS) means for each treatment group with standard errors (SEs), and LS mean differences between treatment groups with corresponding 95% confidence intervals (CIs). The p-values comparing treatment differences will also be presented.

For integrated analyses of Part 1 and Part 2 for Cohorts D1 and D2, treatment groups will be defined as Early-start BIIB105 (i.e., those who initiated BIIB105 in Part 1) and Placebo/Delayed-start BIIB105 (i.e., those who received placebo in Part 1), with baseline defined as Part 1 baseline. Clinical function data will be presented by the 120 mg dose level and treatment group (Cohort D1+D2 Early-start vs Placebo/Delayed-start). They will also be presented by cohort and treatment group as a sensitivity analysis (Cohort D1 Early-start vs Placebo/Delayed-start; Cohort D2 Early-start vs Placebo/Delayed-start).

[figure not shown]

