5.6. Efficacy Endpoints

5.6.1. General Analysis Methods for Efficacy Endpoints

Covariates

The covariates for the statistical models in the integrated analysis for participants from Cohorts D1 and D2 will be based on Part 1 baseline and will be as follows:

- Corresponding baseline score for the endpoint (continuous)
- Baseline disease duration from onset of symptoms to the first dose of study treatment as derived in Appendix 1, i.e. time since symptom onset in months (continuous)
- Baseline plasma NfL
- Riluzole or Edaravone use which will take 3 levels as follows:
 - Edaravone Use (Edaravone = Yes; Riluzole = Yes OR No)
 - Riluzole Only (Riluzole = Yes and Edaravone = No)

CONFIDENTIAL

The information contained herein may not be used, disclosed, or published without the written consent of Biogen MA Inc.

- Neither (Edaravone = No and Riluzole = No)

Edaravone use may only occur for a very small number of subjects in which case this could cause problems for statistical modelling. If Edaravone use is limited to <5 subjects within the relevant population then riluzole and edaravone use will be combined so that there are only 2 levels:

- Edaravone or Riluzole Use (Edaravone = Yes and Riluzole = Yes; OR Edaravone = Yes and Riluzole = No; OR Edaravone = No and Riluzole=Yes)
- Neither (Edaravone = No and Riluzole = No)

Missing data for individual items in scales

The imputation of individual components of each endpoint are described in Section 5.6.2. Imputation will be performed within a scale for each endpoint by prorating the observed scores at the same visit, for example, if there are missing responses to some of the individual questions on a scale at a given visit the endpoint may only be derived for that visit if there are a certain number of individual items/components with available data. Specific details are provided for each assessment/scale, as this differs across assessments/scales. These imputations within a visit will be performed prior to applying imputations on the endpoint at the visit level (e.g. multiple imputation) and will be applied consistently across visits where required. Multiple imputation will not be applied on an individual item/question within an assessment/scale.

Multiple imputation (MI)

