5.6.5. Time to Event Analyses

Time-to-event endpoints include

- Time to death or permanent ventilation (≥ 22 hours of mechanical ventilation [invasive or noninvasive] per day for ≥ 21 consecutive days)
- Time to death

CONFIDENTIAL

The information contained herein may not be used, disclosed, or published without the written consent of Biogen MA Inc.

- Time to death, permanent ventilation (≥ 22 hours of mechanical ventilation [invasive or noninvasive] per day for ≥ 21 consecutive days), or withdrawal from study due to disease progression.

Time to event endpoints will be summarized using Kaplan-Meier curves based on randomization in Study 275AS101 Part 1.

Participants without an event will be censored at the last known alive dates, defined as the interim cut date for 275AS101 (March 12, 2024) or as the last date in the database with any actual study visit or measurements indicating their alive status.

Summary of time-to-event data will be presented by treatment group including number of participants with the event (separate by each individual event for composite event) and number of participants who were censored. Kaplan-Meier plots will be presented. The median survival time, percentiles (5th, 10th, 25th, 75th) and associated 95% confidence limits, and proportion of participants with an event at a list of time points (Week 26, 52, 78, etc.) will be estimated using the Kaplan-Meier. Treatment comparison for time to event will be based on a log rank test. A Cox proportional hazards model will be used to obtain the hazard ratio and 95% confidence intervals. The Cox proportional hazards model may include covariates such as baseline disease duration since symptom onset, baseline plasma NfL, and riluzole or edravone use (as specified in Section 5.6.1 under Covariates). P-value from the log rank test of the survival function will be provided. Hazard ratio (and corresponding 95% CI) comparing the treatment group will be obtained from Cox proportional hazard model. The log-rank test may be stratified by median baseline plasma NfL.

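### An ALS onset or diagnosis date known only to the year is imputed as 15 January, which overstates disease duration for those participants by about 5.5 months on average if dates are spread evenly over the year

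*SAP*

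**What the plan says.** Part 1 SAP, Appendix 1, computes time since onset in months as ("date of first dose received – date of ALS symptom onset)/30.4375", and time since diagnosis in the same way. Its rule for incomplete dates, which covers onset and diagnosis alike, reads: "missing day will be imputed with 15th and missing month/day will be imputed with January 15th". After a blacked-out derivation it adds: "Partial dates for symptom onset will be handled as defined above".

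Duration is used in these places:

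- Part 1 SAP 5.3 summarises duration since onset and since diagnosis as baseline characteristics.
- Part 1 SAP 5.9 puts it in the ANCOVA for the PD biomarkers, plasma NfL among them: "baseline disease duration since symptom onset, and use of riluzole or edaravone".
- Final SAP (Part 2 and integrated) 5.6.1 lists as a covariate "Baseline disease duration from onset of symptoms to the first dose of study treatment as derived in Appendix 1", continuous and in months. This model gives the Week 40 comparisons in 5.6.2 to 5.6.4.
- Final SAP 5.6.5 makes it optional in the Cox model, which "may include covariates such as baseline disease duration since symptom onset, baseline plasma NfL". Protocol 13.3.4 is equally permissive for the clinical function ANCOVA, naming "duration from onset of symptoms to the first dose of study treatment, and riluzole or edaravone use" among possible covariates.

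The visible text sets no limit on the imputed date, does not require diagnosis to follow onset, plans no sensitivity analysis for the rule, and does not say how many dates are known only to the year.

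**The concern.** The two halves of the rule do not match. A missing day goes to the middle of the month and is as likely to be early as late. A missing month goes to the start of the year, so nearly every true date in that year lies after the imputed one and the computed duration is too long.

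The two dates are also filled independently. If onset is known to be June 2021 and diagnosis is known only as 2021, onset becomes 15 June and diagnosis becomes 15 January, five months before onset. Both durations are tabulated, so such a contradiction would show in the baseline output.

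At stake are the accuracy of the baseline description and the quality of the adjustment for disease duration in the plasma NfL analysis, a secondary endpoint of Part 1.

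**Working it through.** The SAP states no figure for this error, so there is none to reproduce.

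**Inputs.** The imputed date (15 January) and the divisor 30.4375 come from Part 1 SAP Appendix 1. Assumption: the true date is equally likely to be any day of the known year.

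**Error for one year-only date.** If the true date is day *d* of a 365-day year, duration is overstated by (*d* − 15)/30.4375 months.

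- Mean: the average *d* is 183, so (183 − 15)/30.4375 = 168/30.4375 = 5.52 months (5.54 in a leap year).
- Range: (1 − 15)/30.4375 = −0.46 to (365 − 15)/30.4375 = +11.50 months.
- Share of dates giving an overstatement: 350/365 = 95.9%.
- SD 3.46, so RMSE = √(3.46² + 5.52²) = 6.5 months.

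**Comparison rules.** Imputing 2 July (day 183) gives mean error 0 and RMSE 3.46 months; 1 July gives +0.03. The missing-day half of the SAP's rule has a mean error of only 0.02 months.

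**When the date must precede a cut-off in the same year** (for onset: diagnosis, Screening or first dose), with dates uniform up to day *n*, the mean is ((*n* + 1)/2 − 15)/30.4375:

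| Latest possible date | *n* | Mean overstatement (months) |
|---|---|---|
| 31 March | 90 | (45.5 − 15)/30.4375 = 1.0 |
| 30 June | 181 | (91 − 15)/30.4375 = 2.5 |
| 30 September | 273 | (137 − 15)/30.4375 = 4.0 |
| 31 December | 365 | 5.5 |

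**Effect on a group and on the covariate.** Let *f* be the share of participants with a year-only onset date. The documents do not give it, so 5% to 20% is assumed. The group mean shifts by 5.52*f*. Treating the other dates as exact, the covariate error variance is *f* × 3.46² + *f*(1 − *f*) × 5.52² under the SAP rule and *f* × 3.46² under mid-year imputation. The ratio is 1 + (1 − *f*) × 30.47/11.97.

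| *f* (assumed) | Shift in mean (months) | Error variance, SAP rule | Error variance, mid-year | Ratio |
|---|---|---|---|---|
| 5% | 0.28 | 2.05 | 0.60 | 3.4 |
| 10% | 0.55 | 3.94 | 1.20 | 3.3 |
| 20% | 1.10 | 7.27 | 2.39 | 3.0 |

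**The case against.** The strongest reply is that this is a convention with little consequence.

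- **An offset shared by everyone does no harm in a linear model.** The intercept absorbs it. If every date were year-only (*f* = 1), the ratio above would be 1 and 15 January would adjust as well as 1 July. This stands: the RMSE of 6.5 months is not by itself a measure of lost adjustment. Only the contrast between year-only and fully dated participants adds error.
- **Year-only dates may be few.** Exclusion criterion 19 uses the months from onset to Screening, so sites needed a usable onset date for Cohorts A, B and C1. This stands in part: the criterion does not apply to C2, D1 or D2.
- **5.5 months is the figure without constraints.** This stands; the smaller values for constrained years are given above.
- **Time since diagnosis is descriptive only.** It is not a covariate in any visible model.

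A reader might infer three stronger things that the documents do not support. The first is that the Week 40 and Cox results certainly carry the error. The final SAP's Appendix 1 is not in the supplied text, so use of the same rule there is only inferred from the cross-reference in 5.6.1, and duration is optional in the Cox model. The second is that a pre-screening slope is made to look slower. The Appendix 1 derivation before "Partial dates for symptom onset will be handled as defined above" is redacted, so whether and how it uses the imputed date cannot be read. The third is that the treatment comparison is materially biased. The covariate is fixed before treatment and the rule is identical in all arms, so nothing here shows that.

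**Conclusion.** The point holds as a minor one. For year-only dates, Part 1 SAP Appendix 1 overstates time since onset or diagnosis almost always, though not always, since a true date of 1 to 14 January gives the opposite error. The average is about 5.5 months if dates are uniform over the year, and less where the date must fall early in that year.

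The error certainly affects the Part 1 baseline summaries and the duration covariate in the plasma NfL ANCOVA wherever such dates exist. In that model the cost is a covariate error variance about 3 times that of mid-year imputation, for an assumed 5% to 20% of year-only dates. The effect on the treatment difference is probably small. The true number of year-only dates is the main unknown.

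**What to change.** Keep the 15th for a missing day. Replace the 15 January rule in Appendix 1 with the midpoint of the interval in which the date can lie:

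- **Onset:** from 1 January of the known year to the earliest of 31 December, the diagnosis date and Screening.
- **Diagnosis:** from the later of 1 January and onset to the earlier of 31 December and Screening.

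With no limit in force this gives about 1 July. The limits are needed because a plain 1 July can fall after a known diagnosis, Screening or first dose. They also keep diagnosis on or after onset. Where both dates are year-only in the same year, state the order, for example onset first and then diagnosis from the imputed onset.

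Report the number of year-only onset and diagnosis dates by treatment group. Confirm that the final SAP's Appendix 1 carries the same rule as the corrected Part 1 SAP.

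Cost: two or three sentences and a few lines of code. If outputs have been run (the final SAP's introduction refers to Part 1 results), rerun the affected baseline summaries and ANCOVA once. If there are no year-only dates, a sentence saying so is enough.
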